6.9 Incidental findings

There will be no clinical testing of samples other than to measure the biomarkers to determine subphenotype. Similarly, there are no additional clinical examinations other than routine clinical examination as part of standard care. Therefore, there will be no incidental findings reported to the patient, their clinical care team or their primary care physician.

7. TREATMENTS

7.1 Interventions

Patients will receive usual care or usual care plus the intervention as allocated by randomisation.

Details about the intervention are included in the relevant intervention specific appendix.

7.2 Concomitant Care

Any treatment decisions not outlined in the PANTHER protocol will be left to the judgement of the treating clinician.

7.3 Investigational Medicinal Product Details

Any IMP which has marketing authorisation in the relevant country and is stocked by the site hospital pharmacy, may be employed in this trial.

Interventions that do not have a marketing authorisation in the relevant country will be provided to sites. Details of this supply will be provided in the relevant intervention appendix.

The Summary of Product Characteristics (SmPC) for each approved IMP (or investigator brochure (IB) for unapproved IMP) is provided as a separate document and is filed in the TMF. This is a representative SmPC/IB. The Reference Safety Information within the relevant SmPC/IB is used for drug safety and other reference in this trial. The SmPC/IB will be reviewed annually for potential updates.

The IMP risk classification (or equivalent) for the trial will be completed in each country. The IMP risk classification may vary by country. Labelling and packaging requirements will depend on this classification. See below for illustration purposes. Note the term 'classification' may vary by country, see region specific appendix for clarification.

- Classified as a Type A risk (or equivalent), any potential risk is no higher than that of standard medical care. No specific labelling required.
- Classified as a Type B (or equivalent), somewhat higher than the risk of standard medical care. Full labelling may be required.
- Classified as a Type C (or equivalent), markedly higher than the risk of standard medical care. Full labelling may be required.

Confidential Page 23 of 48

London

7.4 Permanent Discontinuation of Study Treatment and Withdrawal from Study

(i) Permanent discontinuation of study treatment

Participants may discontinue study treatment for the following reasons:

- At the request of the participant or consenting legally authorised representative (LAR)
- Serious Adverse Event related to the study drug
- Allergic reaction to IMP
- Decision from the attending ICU physician that the study drug should be discontinued on safety grounds.
- If advised by the international trial steering committee based on advice from the DMC

Withdrawal from Study (ii)

Withdrawal from the study refers to discontinuation of study treatment and study procedures and can occur for the following reasons:

- Participant decision
- Loss to follow-up

Procedures for Withdrawal from Study (iii)

Patients will be free to withdraw at any time. If the patient (or their personal/professional legal representative) wishes to withdraw from the study during the treatment period, the treating physician will no longer follow the trial protocol and the study drug will be stopped. If the participant withdraws from the study this will be documented in the eCRF and medical records.

The patient will be able to either withdraw completely from the trial or from certain elements. Further follow-up as part of the clinical trial will cease. However, the participant will be asked if data collection through routine locally collected clinical data and data linkage, including long-term follow-up can continue.

Participants will be asked if previously collected, stored blood samples can be used for further analyses or if they would prefer their samples to be destroyed.

In the rare situation where the patient is discharged from hospital prior to obtaining consent, the most appropriate member of the site research team (who is also part of the direct care team) will attempt at least one phone call to the patient to inform them of their involvement in the study, provide information about the study and obtain their verbal consent. Following on from the call, or if there is no response to the call, the patient will be sent a covering letter, personalised by the most appropriate member of the site research team (who is also part of the direct care team) or clinical staff member, and a copy of the PIS and Consent Form (postal versions) by post. The letter will direct the patient to the PIS for detailed information on the study and provide telephone contact details if the patient wishes to discuss the trial with a member of the site research team. It will also explain the option to provide consent electronically by completing the online e-consent form if feasible in the region.

If consent to continue is not obtained despite these attempts, data already collected will not be deleted as these will include important safety information which would be processed as part of a legitimate interest.

Confidential Page 24 of 48 Protocol No: 175151 Sponsor: Imperial College

London

V 2.1 30.07.2025

8. PHARMACOVIGILANCE

8.1 Adverse Event (AE)

An AE is any untoward medical occurrence in a patient or clinical trial participant administered a medicinal product and which does not necessarily have a causal relationship with this treatment. An AE can therefore be any unfavourable and unintended sign (including an abnormal laboratory finding), symptom, or disease temporally associated with the use of the trial medication, whether or not considered related to the IMP.

8.2 Adverse Reaction (AR)

All untoward and unintended responses to an IMP related to any dose administered. All AEs judged by either the reporting investigator or the sponsor as having reasonable causal relationship to a medicinal product qualify as adverse reactions (ARs). The expression reasonable causal relationship means to convey in general that there is evidence or argument to suggest a causal relationship.

8.3 **Unexpected Adverse Reaction**

An AR, the nature or severity of which is not consistent with the applicable product information as set out in the Reference Safety Information (RSI) (in the investigator's brochure for an unapproved investigational product or summary of product characteristics (SmPC) for an authorised product).

When the outcome of the adverse reaction is not consistent with the applicable product information this adverse reaction should be considered as unexpected. Side effects documented in the RSI section of the SmPC/IB which occur in a more severe form than anticipated are also considered to be unexpected.

Expectedness assessment will be performed by the Sponsor or person delegated by the Sponsor to assess expectedness.

8.4 Causality

The assignment of causality for adverse events should be made by the investigator responsible for the care of the participant using the definitions in the table below.

If any doubt about the causality exists the local investigator should inform the study coordination centre who will notify the Chief Investigator. The pharmaceutical companies and/or other clinicians may be asked to advise in some cases.

Unrelated: No evidence of any causal relationship

There is little evidence to suggest there is a causal relationship (e.g. the Unlikely:

event did not occur within a reasonable time after administration of the

trial

medication). There is another reasonable explanation for the event (e.g.

the patient's clinical condition, other concomitant treatment).

Possible:

the

There is some evidence to suggest a causal relationship (e.g. because

event occurs within a reasonable time after administration of the trial

Confidential Page 25 of 48 Protocol No: 175151 Sponsor: Imperial College V 2.1 30.07.2025 London

medication). However, the influence of other factors may have

contributed

to the event (e.g. the patient's clinical condition, other concomitant

treatments).

Probable: There is evidence to suggest a causal relationship and the influence of

other factors is unlikely.

Definite: There is clear evidence to suggest a causal relationship and other

possible

contributing factors can be ruled out.

8.5 Severity of Adverse Events

Mild: Awareness of event but easily tolerated

Moderate: Discomfort enough to cause some interference with usual activity

Severe: Inability to carry out usual activity

8.6 Adverse Event recording

As this is a trial is conducted in critically ill patients with life-threatening critical illness then adverse events are expected to occur regularly in most, if not all, patients regardless of treatment assignment. Events that that are expected in this population i.e. events related to the underlying critical illness will not be reported as adverse events. In addition, unless an adverse event is assessed to meet Serious Adverse Event criteria these adverse events will not be reported in the case report form and simply noted in the patient's local medical record. Any additional reporting will be detailed in the RSA and ISA.

8.7 Abnormal Laboratory Test Results

Similarly due to the nature of the underlying critical illness, abnormal laboratory test results will be expected to occur daily for most, if not all, patients and therefore do not need to be reported as an AE/AR in the CRF. They will be recorded in the patients' medical record. Any clinically important abnormal laboratory tests will be repeated at appropriate intervals until they return either to baseline or to a level deemed acceptable by the local investigator.

8.8 Serious Adverse Events (SAE)

(i) Definition of SAE

An SAE is defined as any event that

- Results in death:
- Is life-threatening*;
- Requires hospitalisation or prolongation of existing inpatient's hospitalisation**;
- Results in persistent or significant disability or incapacity;
- Is a congenital abnormality or birth defect;

Confidential Page 26 of 48

^{* &}quot;Life-threatening" in the definition of "serious" refers to an event in which the participant was at risk of death at the time of the event; it does not refer to an event which hypothetically might have caused death if it were more severe.

^{** &}quot;Hospitalisation" means any unexpected admission to a hospital department. It does not usually apply to scheduled admissions that were planned before study inclusion or visits to casualty (without admission).

London

Medical judgement should be exercised in deciding whether an adverse event/reaction is serious in other situations. Important adverse events/reactions that are not immediately lifethreatening, or do not result in death or hospitalisation but may jeopardise a subject, or may require intervention to prevent one of the other outcomes listed in the definition above should also be considered serious.

Reporting of SAEs (ii)

The primary and secondary outcomes have been selected to capture the most commonly occurring safety events in critically ill patients (e.g. mortality, organ failure and support). Therefore, any events that are captured as an outcome in the eCRF do not require reporting as an SAE unless in the opinion of the local PI the event was attributable to a study intervention / IMP or the trial protocol.

Rapid reporting of all SAEs i.e. within 24 hours, occurring during the patient's ICU stay up to a maximum of 28 days must be performed as detailed in the study-specific safety reporting instructions.

Active monitoring of participants after discharge from ICU or after 28 days is not required, but if the investigator becomes aware of safety information that appears to be drug or trial related, involving a participant who participated in the study, even after an individual participant has completed the study, this should be reported to the Sponsor.

All SAEs will be reviewed by the Chief Investigator or a designated medically qualified representative to confirm expectedness and causality.

Reporting of SAEs and review by the CI will be via the trial data collection system (CRF/eCRF).

Definition of a Serious Adverse Reaction (SAR) (iii)

A SAR is defined as a SAE that is judged to be (possibly, probably or definitely) related to any dose of study drug administered to the participant.

Definition of Suspected Unexpected Serious Adverse Reaction (SUSAR) (iv)

Any SAR that is NOT consistent with the applicable product information as set out in the Reference Safety Information (RSI) section of the Investigator Brochure (IB) or Summary of Product Characteristics (SmPC).

(v) Reporting of SUSARs

SUSARs should be notified to the appropriate regulatory authority, the relevant EC and the Sponsor in accordance with regulatory requirements. SUSARs which are fatal or lifethreatening will be reported not later than 7 days after alerting the sponsor to the reaction. Any additional relevant information will be sent within 8 days of the report. A SUSAR which is not fatal or life-threatening will be reported within 15 days of first knowledge by the sponsor. The sponsor will inform all investigators about SUSARs occurring on the study.

Follow up of participants who have experienced a SUSAR should continue until recovery is complete or the condition has stabilised.

Confidential Page 27 of 48

SUSAR reports will be unblinded prior to submission if required by national regulatory requirements.

SUSARs reported in one region may be required to be reported in another, further details of this will be provided in the RSAs.

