6.3 Randomisation and Blinding

The trial is open-label whereby participants, the clinical team and study team will not be masked to the interventions. To avoid bias during the ongoing PANTHER platform, where possible, modifications will be made. Only the unblinded trial statisticians will have access to emerging aggregate data and results by treatment allocation until interventions are stopped. These statisticians will be responsible for carrying out the adaptive analyses and construction of all statistical reports for regular DMC meetings.

Confidential Page 19 of 48

Each participant will be assigned a unique trial ID which is linked to their treatment allocation.

Bias will be minimised by the following:

Detection and performance: The primary outcome and most of the secondary outcomes are objective outcomes that will be unaffected by knowledge of treatment allocation. The unblinded trial statistician undertaking the planned adaptive analyses will not be involved in design decisions of the ongoing platform. Delivery of usual care based on international guidelines will decrease the likelihood of performance bias. No aggregate data by intervention will be available to the study team throughout the trial prior to any statistical trigger being met and final analysis.

Selection bias: Treatment allocation will be concealed prior to randomisation using an automated online system. To ensure clinicians have equipoise, we will evaluate screening logs and examine reasons why patients have not been enrolled into the study.

Attrition bias: The primary outcome along with most other outcome data will be collected during the hospital stay. Data on mortality will be derived electronically from routinely collected health data sources where possible. Experience from previous trials indicates missing outcome data for the primary outcome and mortality to day 90 will be minimal both in the UK and at international sites. Withdrawal rates are typically <5% in critical care trials (10,11). We will seek participants' (or their representatives'), permission to retain data collected up until the time-point that they choose to withdraw. This will maximise primary and secondary outcome data acquisition. Our experience in the UK and internationally is that patients normally agree to proceed on this basis.

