6.8 Research samples

Research samples will be collected as described in the sample handling manual. In summary there is a tiered approach to the collection of research samples and will include: -

- 1) blood samples for phenotyping, plasma, serum and RNA on the day of but prior to randomisation, day 2 and day 6.
- 2) blood samples for cell isolation on the day of randomisation and day 2.
- 3) tracheal aspirate samples on the day of randomisation, day 2 and day 6 (if intubated).
- 4) a nasopharyngeal swab on the day of randomisation and
- 5) a bronchoalveolar lavage sample in selected sites on the day of randomisation and day 2.

Details of the processing, handling and shipping are provided in the sample handling manual. The samples will be sent to a regional central laboratory for storage and analysis to understand the mechanism of effect of the interventions and heterogeneity of treatment effect as well as use in ethically approved studies.

Confidential Page 22 of 48

If resources prevent collection of the research samples this is not a protocol deviation.

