Estimands for analysis of secondary efficacy endpoints will use the same treatment conditions, the same population, and intercurrent events and strategies to handle these, apart from the outcome 'Progression to invasive mechanical ventilation, extracorporeal membrane oxygenation or death' which will use the population consisting of those participants not intubated at baseline and the handling of mortality which will alter depending on the nature of the outcome and its interpretation in relation to death, and length of stay which will use the population who survived. The outcome variable and population-level summary measure will vary as appropriate for each endpoint. All secondary estimands will be specified in the SAP.

Treatment effects for final analysis will be estimated using a regression modelling approach in a Bayesian framework with vague priors. Adjustment for baseline values will be used where suitable.

Analysis of ordinal secondary outcomes (days free of vasopressor or respiratory support) will be as per the primary outcome. Analysis of binary outcomes at single time points will use logistic regression. Analysis of continuous outcomes will use linear regression.

Posterior mean contrasts (differences, odds ratios, incidence rate ratios) between treatment groups will be reported together with 95% credible intervals. Model assumptions will be examined using residual analysis including examination of graphical displays such as normal quantile plots.

Serious Adverse events

In addition to the information on safety provided by the adaptive analyses of the primary and secondary outcomes, cumulative data on SAEs will be presented to the Data Monitoring Committee on a regular basis.

As there is monitoring of important safety outcomes through primary and secondary outcomes (eg mortality, organ support), these events will not be recorded as SAEs as described above. All other SAEs will be tabulated by arm and compared between arms through calculation of incident rate ratios (IRR) and 95% credible intervals (CI).

Confidential Page 33 of 48

London

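### The SAE rate ratio in section 9.6 does not clearly leave out outcome events that become SAEs only when an unmasked investigator attributes them to treatment or protocol, so it may exceed 1 without true harm

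*Protocol*

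**What the plan says.** **Reporting rule.** Section 8.8 (ii) of the protocol says that an event captured as an outcome in the eCRF need not be reported as an SAE "unless in the opinion of the local PI the event was attributable to a study intervention / IMP or the trial protocol". SAEs are to be reported rapidly during the ICU stay, up to a maximum of 28 days. After that there is no active monitoring, but a report goes to the sponsor "if the investigator becomes aware of safety information that appears to be drug or trial related".

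**Masking and control.** Section 6.3: "The trial is open-label whereby participants, the clinical team and study team will not be masked to the interventions". Section 7.1: "Patients will receive usual care or usual care plus the intervention as allocated by randomisation". There is no placebo.

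**Analysis.** Under Serious Adverse events, section 9.6 notes that mortality, organ support and similar events are monitored through the outcomes and that "these events will not be recorded as SAEs as described above". It continues: "All other SAEs will be tabulated by arm and compared between arms through calculation of incident rate ratios (IRR) and 95% credible intervals (CI". Cumulative SAE data go regularly to the DMC.

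**Related text.** Section 8.8 (iii) defines a serious adverse reaction as an SAE judged related to study drug. Section 3.5 names SAEs as a secondary endpoint (ix) and, separately, lists safety outcomes (viii) such as stroke, venous thromboembolism, myocardial infarction and serious infection.

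**The concern.** Whether an outcome-type event becomes an SAE depends on a causality opinion from someone who knows the allocation. Part of that opinion, attribution to an intervention or IMP, cannot apply to a participant on usual care alone. The same stroke or bloodstream infection can therefore be an SAE in an active arm and not in usual care, with no difference in how often it occurs.

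That does no harm in a reporting rule, whose purpose is to find suspected reactions. It matters if the resulting records are the numerator of a between-arm rate ratio. The IRR would then mix event frequency with readiness to attribute, and would be expected to point against the active arm. The DMC sees these data while deciding whether to act on stopping triggers that section 9.4 makes non-binding.

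**Working it through.** **Step 1: do the attributed events enter the IRR?** Two readings of section 9.6 are possible.

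- *They enter.* The sentence that takes outcome events out of SAE recording refers back to the rule already described. That rule is section 8.8 (ii), which contains the attribution exception. Section 8.8 (iii) makes a serious adverse reaction a subset of SAEs, so an attributed outcome event must be an SAE to reach SUSAR reporting. It is then in the SAE data and is compared unless expressly removed.
- *They do not enter.* The sentence is taken at face value: outcome events are not SAEs, and only the remainder is compared. Section 9.6 then contradicts section 8.8, under which some outcome events are SAEs.

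The first is the more natural reading. Neither is stated.

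**Step 2: expected IRR with no true drug effect, if they enter.** The protocol states no SAE rate, IRR or attribution share, so there is no figure to reproduce. Assume equal follow-up in both arms and let

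- r0 = non-outcome SAEs per participant, same in both arms (assumed 0.05 to 0.30);
- q = outcome-captured events per participant, same in both arms. The only anchor is the ARDS mortality of up to 30-50% in section 2, which gives 0.3 to 0.5 for deaths alone;
- a, b = share of outcome events attributed in the active and usual care arms (assumed 2% to 10%, and 0% to 5%).

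Expected IRR = (r0 + a·q) / (r0 + b·q), which exceeds 1 whenever a > b.

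For r0 = 0.10 and q = 0.5:

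| a | b | Calculation | IRR |
|---|---|---|---|
| 5% | 0% | (0.10 + 0.025) / 0.10 | 1.25 |
| 5% | 1% | (0.10 + 0.025) / (0.10 + 0.005) | 1.19 |
| 5% | 5% | 0.125 / 0.125 | 1.00 |

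Over the ranges for r0 and q, with b = 0:

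| a | Lowest (r0 = 0.30, q = 0.3) | Highest (r0 = 0.05, q = 0.5) |
|---|---|---|
| 2% | 0.306 / 0.30 = 1.02 | 0.06 / 0.05 = 1.20 |
| 5% | 0.315 / 0.30 = 1.05 | 0.075 / 0.05 = 1.50 |
| 10% | 0.33 / 0.30 = 1.10 | 0.10 / 0.05 = 2.00 |

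**Step 3: chance of a false signal.** Take Poisson counts x1 (active) and x0 (usual care), equal arm sizes, and a Beta(x1 + 0.5, x0 + 0.5) posterior for the active arm's share of events. The IRR exceeds 1 when that share exceeds 0.5. For the IRR of 1.25 above:

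| n per arm | Expected counts, active v usual care | Chance that lower 95% bound exceeds 1 |
|---|---|---|
| 80 (first adaptive analysis) | 10 v 8 | 7% |
| 504 (hypoinflammatory cap) | 63 v 50.4 | 22% |

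The nominal figure is 2.5%.

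**Step 4: after the fix.** With outcome-captured types left out of the IRR, both arms have rate r0 and the expected null IRR is 1.00. The chance that the lower bound exceeds 1 is 2.3% to 2.7% at 80 per arm and 2.5% at 504.

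**The case against.** **Section 9.6 may already exclude these events.** This is a fair reading, and under it the IRR is not biased by this route. It still leaves section 9.6 at odds with section 8.8, so the text needs settling either way.

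**Detail may sit in the SAP, which is not at hand.** Section 9.6 does defer SAE detail, but names death, non-adherence and other effective medications as the issues to be handled there. The difficulty here comes from how two protocol sections fit together.

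**The same events are compared without any attribution filter.** This stands. Section 9.4 presents secondary and safety outcomes by treatment group, and the formal triggers use only the primary-outcome odds ratio. The DMC has a clean comparison of these events beside the IRR, and the problem is confined to the IRR.

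**Causality is reviewed centrally.** Section 8.8 provides this for reported SAEs. No step is stated for outcome events left unreported in usual care.

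**Stronger readings the documents do not support.** A reader might infer that:

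- *an outcome event becomes an SAE only through drug attribution.* The rule also names the trial protocol. That route is open to usual care, for example through "a bronchoalveolar lavage sample in selected sites on the day of randomisation and day 2", which section 6.8 does not limit to active arms;
- *the IRR is shown to be biased against every intervention.* That requires the first reading of section 9.6 and more frequent attribution in each active arm, and the protocol documents neither;
- *later reports after ICU discharge inflate the IRR too.* Section 8.8 sends them to the sponsor and does not say that they enter the analysis.

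The arithmetic also counts every attributed event as serious. Some listed outcomes are laboratory thresholds, which need not meet the seriousness criteria.

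**Conclusion.** The point holds in a conditional form. SAE ascertainment for outcome-type events depends on arm, and section 9.6 does not clearly keep those events out of the rate ratio. If they enter, the expected IRR exceeds 1 without true harm whenever attribution is more frequent in active arms, which is likely where one arm has no drug to attribute to. The size cannot be known from the protocol: 1.02 to 2.00 across the assumed values with no attribution in usual care, 1.25 in the worked example, and 1.00 if attribution is equal or the events are excluded. It should be corrected, because the ambiguity affects a named secondary endpoint shown to the DMC and is cheap to remove.

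**What to change.** Keep the attribution exception in section 8.8 unchanged for expedited and SUSAR reporting. In section 9.6 and the SAP, state that:

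- the between-arm SAE IRR counts only event types not captured as eCRF outcomes, whatever the attribution, within the section 8.8 reporting window (ICU stay, maximum 28 days);
- outcome-type events are compared through the outcome data in all arms;
- outcome events attributed by the investigator, and any later drug- or trial-related reports, are listed separately by arm without a rate ratio.

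Reword the sentence in section 9.6 on what is not recorded as an SAE so that it acknowledges the exception in section 8.8.

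The cost is a few sentences and no new data. The downside is that attributed outcome events appear in a listing and not in the IRR.
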